#### Experiences of living with a stoma

- In terms of stoma symptoms or problems did you have any expectations before your surgery? (*Prompt: Where did these come from?*)
- How has stoma/area around the stoma been? (Prompt: Any issues/complications?)
- How have you found managing your stoma and the area around your stoma? (Prompt: What liked?)
- Have you had to go back to hospital because of any problems with the stoma or area surrounding the stoma? (*Prompt: Have you needed to go back to theatre or see your surgeon or stoma nurse for any problems?*)
- Do issues relating to your stoma, or area around your stoma, bother or worry you on a day-day basis? (*Prompt: Commonly experienced problems such as pain, redness or skin problems*)
- Are there any quality of life issues related to the stoma, or area around your stoma? (*Prompt: In what way can having a stoma affect your quality of life e.g. smell, leakage fears, time costs*)
- Do issues relating to your stoma, or area around your stoma, affect your social life? (*Prompt: Limitations to work, time costs, financial issues, sexual issues, social issues*)
- Do you have any additional support needs because of issues relating to you your stoma, or area around your stoma? (*Prompt: e.g. Carers, family/friend support, GP appointments, referrals to clinic, referrals to A&E, stoma nurse follow-ups, district nurse follow-ups, social work, emotional support, psychological support)*

- Are there any financial issues related to your stoma, or area around your stoma? (*Prompt: Cost of bags, cleaning, laundry*)
- Do you find that issues with your stoma, or area around your stoma, affects you emotionally? (*Prompt: Such as depression, relationship problems, social anxiety*)
- Are there any work related issues with your stoma, or area around your stoma? (*Prompt: Disability days, change in responsibilities, confidence in the work place*)
- Does your stoma, or area around your stoma, affect your ability to participate in normal activities? (E.g. Shopping, exercising, socialising, enjoying family time, maintaining relationships)
- Are you known to have a PSH?

## Persepectives of questionnaire

We are developing a questionnaire that aims to understand patients' of living with a stoma that may or may not be complicated by the presence of a parastomal hernia.

- Would you kindly complete this questionnaire and comment on how understandable the questions are and whether you think the questions cover all symtpms and problems of having a stoma/PSH.
- Can you add anything?

## Closing

- Summarise key points
- Any further questions?

(Thank you, Recorder OFF)

Comments:

### Appendix IV: Distress protocol: Interviews

All interviews will be prefaced with a statement about confidentiality and the duty of care. Participants will be told that the interview is strictly confidential but should they disclose information to suggest that they are at significant risk of harm the researcher may have to discuss this with a clinical advisor.

In the event that a participant appears to be distressed during the interview (for example, becomes silent or begins to cry) or discloses information to provoke concern about suicide risk, the following procedures will be followed:

- 1. Participants will be offered the opportunity to pause for a break from the interview and will be asked if they would like to resume the interview
- 2. If necessary, the interview will be terminated and recording equipment will be stopped
- 3. At first, the interviewer will listen to the interviewee and offer support in situ. This will allow the researcher to assess whether further action is required
- 4. Should the interviewer remain concerned, they will reflect this to the interviewee and, depending on the nature of the situation:
  - a. Offer information about local sources of help
  - b. Ask the interviewee if there is anyone they should contact, and if so attempt to make contact
  - c. Offer to make initial contact with clinical services (primary or secondary care) on behalf of the individual and with their consent
- 5. In cases of particular concern, the interviewer will
  - a. If necessary, remain with the person until their distress has subsided or someone else is present
  - b. Contact a local study clinician for advice or assistance
  - c. Provide a written report of the incident to the principal investigator including information about the nature of the distress and the actions taken

Interviewees will be advised to contact their GP should they subsequently find that the interview provokes issues that they need to discuss.

#### Appendix V: Letter 2: GP notification Interviews

The CIPHER Study University of Bristol School of Social & Community Medicine, [name]

Private and confidential

Dear General Practitioner,

Re: <insert patient name, date of birth & address>

We would like to inform you of the above patient's involvement in the UK Cohort study to Investigate the prevention of Parastomal HERnia (CIPHER) Phase A. We will be interviewing the above patient about living with a stoma. During the interviews if any parastomal hernias or medical problems are detected, that have not already undergone investigation we may write to you to request that a clinical appointment with yourself or their normal team be made to investigate and discuss it further.

This study is being run by the University of Bristol in conjunction with the Royal Devon and Exeter & University Hospitals Bristol NHS Foundation Trusts. Please contact us with any concerns,

Yours faithfully,

[name] BSc, [name] Chief investigator of the CIPHER study Phase A, Professor of Surgery at the University of Bristol Consultant Upper GI Surgeon at the Bristol Royal Infirmary

#### Appendix VI: Letter 3: GP notification case studies

The CIPHER Study University of Bristol School of Social & Community Medicine, [name]

Private and confidential

Dear <insert GP name>

Re: <insert patient name, date of birth & address>

We would like to inform you of the above patient's involvement in the UK Cohort study to Investigate the prevention of Parastomal HERnia (CIPHER) Phase A. We will be observing and digitally recording the above patient's stoma formation in theatre. This study is being run by the University of Bristol in conjunction with the Royal Devon and Exeter NHS Foundation Trust, University Hospitals Bristol NHS Foundation Trust and University Hospital Birmingham NHS Foundation Trust. Please contact us with any concerns,

Yours faithfully,

[name] BSc, [name] Chief investigator of the CIPHER study Phase A, Professor of Surgery at the University of Bristol Consultant Upper GI Surgeon at the Bristol Royal Infirmary

## Glossary / abbreviations

ACPGBI	The Association of Coloproctology of Great Britain and Ireland
CI	Chief Investigator
CONSORT	Consolidated Standards of Reporting Trials
CRF	Case Report Form
СТ	Computerised Tomography
CTEU	Clinical Trials and Evaluation Unit
EHS	European Hernia Society
HES	Hospital Episode Statistics
HRQoL	Health-related Quality of Life
ICH-GCP	International Conference for Harmonisation of Good Clinical Practice
ICU	Intensive Care Unit
IEP	Image Exchange Portal
ISRCTN	International Standard Registered Clinical Trial Number
MDT	Multi-Disciplinary Team
MRC	Medical Research Council
MRI	Magnetic Resonance Imaging
NHS	National Health Service
NICE	National Institute for Health and Care Excellence
NIHR	National Institute for Health Research
ONS	Office of National Statistics
PIL	Patient Information leaflet
PPI	Patient Public Involvement
PSS	Patient Social Services
PROs	Patient Reported Outcomes
PSH	Parastomal Hernia
QALY	Quality-adjusted Life Year
RCT	Randomised Controlled Trial
REC	Research Ethics Committee
SAP	Statistical Analysis Plan
SCN	Stoma Care Nurse
SEG	Study Executive Group
STCs	Surgical Trainee Collaboratives
SSC	Study Steering Committee

## 1. Study summary

During abdominal surgery, it is sometimes necessary to create a stoma to divert faeces from the bowel into an external pouch or bag. Unfortunately, the formation of the stoma can be associated with future complications, including the risk of developing a parastomal hernia (PSH). A PSH is an incisional hernia, immediately adjacent and related to the stoma, that occurs when the fascia in the abdominal wall splits. Contents of the abdomen, e.g. fatty tissue or intestine, can be forced through the split in the fascia causing a bulge in the skin. PSH are relatively common and affect approximately 40% of patients within 2 years of their bowel surgery.

Complications of PSH can be severe and are known to negatively influence patients' quality of life. Specifically, PSH can make it difficult to attach stoma bags which can cause the bag contents to leak and smell, irritate the surrounding skin and make patients anxious and avoid social situations. PSH can also cause pain and serious problems, e.g. bowel obstruction, which need emergency treatment in hospital. PSH are difficult to manage and in most cases treatment involves specialist stoma care with expensive appliances. In some cases, a surgeon may reoperate to repair the hernia but additional surgery is risky and recurrence of a hernia is not uncommon. Therefore, it is very important to prevent a PSH forming in the first place.

Both patient and surgical factors are believed to influence the development of PSH. Of the surgical factors, the size and shape of the incision in the body wall, the use of mesh when the stoma is formed and, if mesh is used, exactly how it is used, have all been described as potentially important considerations. However, the way in which surgeons create stomata is very varied and research is needed to investigate whether these factors influence the risk of developing a PSH. This is the aim of the CIPHER study.

## 2. Background

## 2.1 The clinical problem

The prevalence of all types of abdominal stomata in the UK is about 100,000 and 20,000 new stomata are created annually [1]. However, the incidence of PSH is more difficult to assess due to a lack of prospective data and heterogeneity in how clinical and symptomatic PSH are defined. In the current literature, rates of PSH of up to 40% have been reported, varying according to follow-up duration, stoma type and diagnosis method.

To date a variety of methods have been used to diagnose PSH both clinically and symptomatically. Clinically, PSH has been diagnosed from intra-operative findings, clinical examination and computerised tomography (CT). Clinical examination has poor inter-observer reliability [2] and the European Hernia Society (EHS) considers CT to be best way to detect PSH when following up patients with stomata [3]. However, an 'anatomical' PSH detected by CT may not cause symptoms. Symptomatic PSH have typically been identified from health-related quality of life (HRQoL) assessments but the appropriateness of using particular HRQoL tools to detect problems specific to PSH is uncertain. Regardless of the method of clinical or symptomatic diagnosis, PSH can have substantial physical, psychological and economic consequences.

## 2.2 The burden of PSH

## 2.2.1 The physical and psychological burden of PSH

PSH are common and are symptomatic for at least 75% of patients. Pain (35%), difficulties attaching stoma bags with associated leakage of bowel contents (28%) and peristomal skin irritation are the commonest problems [4]. Bowel strangulation, obstruction and perforation may also be related to PSH and are rare but serious [5]. In addition, PSH reduces HRQoL and causes limitations in sexual function, travel, social interaction and return to work [6]. Despite advances in stoma care, the proportion of patients with symptoms has remained largely unchanged over the past 20 to 30 years [6].

## 2.2.2 The economic burden of PSH

The economic impact of PSH on the NHS is poorly understood because accurate data regarding stomata are difficult and expensive to extract [7]. However, it has been reported that patients with symptomatic stoma are more likely to have increased rates of consultation with community healthcare teams [8], and increased direct costs related to stoma bags and associated products such as belts, adhesives, sprays, wipes and barrier creams. The cost of stoma bags and associated products was over £228m in 2012 in England alone [9] and costs have risen over 30% in the past 5 years. Skin irritation, one of the commonest problems associated with PSH, is estimated to cost an additional 50 Euro per patient over a 7 week treatment period [10]. The cost of bags and accessories for a patient managing a stoma effectively varies between £780 and £1800 per year; this sum can rise to £6000 per year when a PSH is present [11]. Furthermore, none of the estimated costs incorporate the expense and / or time of the approximately 600 stoma care nurses (SCNs) in the UK.

Some PSH may be repaired surgically and emergency surgical intervention is indicated in some circumstances, e.g. if a PSH causes bowel obstruction. The precise number of PSH repair procedures performed annually in the NHS is currently unknown due to variation in coding. PSH repair performed as elective surgery may be recorded alone or as part of a more complex incisional hernia repair; emergency repair may be recorded as part of a laparotomy. Regardless of coding, PSH repair is associated with significant costs including: the patient's in-hospital stay (including in critical care units), theatre time, intra-operative equipment used and the cost of mesh implants. Unfortunately, complications following PSH repair surgery are common and the hernia recurrence rate is high, leading to further interventions [12-14].

## 2.3 Factors influencing PSH development

It is presumed that both surgical factors and patient characteristics can influence the risk of developing PSH. Patient characteristics such as diabetes, obesity and smoking have been linked with compromised tissue healing and, therefore, place patients at a greater risk of PSH. Such factors are also extremely challenging to modify. Surgical factors also have the potential to influence the development of PSH and are more amenable to modification. Such factors may include: the surgical approach (open or laparoscopic); the size, shape and site of the trephine incision in the abdominal wall; route of placement of the bowel

(extraperitoneal or transperitoneal); the use or not of prophylactic mesh at the stoma site and, if mesh is used, how it is used [15].

Of the technical surgical elements elicited above, the use of prophylactic mesh is one of the more widely studied, being the subject of 12 systematic reviews [16-26] and value analyses [27]. The systematic reviews reported that mesh use (compared with no mesh) during initial stoma formation was associated with a lower incidence of PSH. However, it is important to note that the early reviews [24-26] included the same single centre RCTs [28-30], which had methodological limitations. Specifically, these RCTs were small, had limited generalisability, were poorly designed, used different meshes with variable stomata types, varied in follow-up duration and were all at high risk of bias. Subsequent reviews have included more RCTs and concluded similarly that prophylactic mesh results in lower incidence of PSH. However, even the newer RCTs have significant methodological limitations [31] and the findings of these reviews should be interpreted with caution. Better quality multicentre RCTs with longer follow up are ongoing in Europe (PREVENT, STOMA MESH, STOMA CONST).

The costs of mesh vary according to type (e.g. biological mesh for one operation costs about £1000, synthetic mesh less than £20) but, if the more expensive option reduces the risk of PSH or the risk of complications, the post-operative costs should be reduced and a better patient outcome secured. Therefore, it is important to establish the balance of costs and benefits between options for key surgical steps.

The use of prophylactic mesh has also been subject to value analyses which reported that bioprosthetic mesh used during initial stoma construction may be cost effective at reducing the risk of PSH, if the risk of subsequent PSH repair is in excess of 39% [27]. The use of prophylactic synthetic mesh compared to no prophylactic mesh is also associated with lower costs and more Quality Adjusted Life Years (QALYs) for patients with stages I to III rectal cancer but the benefits for patients with stage IV cancer are marginal [32]. However, these conclusions are based on the results of meta-analyses of the effectiveness of mesh, which are themselves uncertain due to the small sample sizes and poor quality of the included trials.

In summary, modification of the technical aspects of surgery may reduce the incidence of PSH and could lead to improvements in the health of patients, better quality of life, a reduction in direct stoma appliance and accessory costs and fewer PSH repairs. The modifications offer the potential for significant savings for the NHS as well as benefit for individual patients. Unfortunately, existing studies on surgical technique relating to stoma formation are limited by poor design and generalisability [24] and, consequently, further high quality research is urgently needed. CIPHER will attempt to address this evidence gap.

## 2.4 Support for the study

The Association of Coloproctology of Great Britain & Ireland (ACPGBI) has prioritised research to investigate ways to prevent PSH [33]. The high priority of the research question has also been recognised by the Colostomy Association (a patient support organisation) and by the Association of SCNs, which both support the CIPHER study.

#### 3. Aims and objectives

The CIPHER study (Phase B; CIPHER-B) aims to establish the incidence of symptomatic and radiologically confirmed PSH during a minimum of 2 years follow up. Additionally, CIPHER aims to evaluate the effects of key technical surgical steps during index stoma formation on the risk of subsequent PSH formation.

Specific objectives of CIPHER-B are:

- 1. To describe the incidence of PSH formation within 2 years of formation of all types of stomata other than loop ileostomies;
- 2. To describe the risk of PSH for different types of stoma (end colostomy versus loop colostomy versus end ileostomy)
- 3. To describe the risk of PSH according to how the stoma trephine is created in the anterior fascia of the abdominal wall with respect to location (within or without the rectus sheath) and shape (cross versus circle versus slit);
- 4. To describe the relative risk of PSH following index stoma creation with or without mesh (no prophylactic mesh versus biologic mesh versus synthetic mesh);
- To describe the relative risk of PSH following index stoma creation with prophylactic mesh according to mesh position (intra-abdominal versus sublay/retrorectus versus. onlay);
- 6. To describe the relative risk of PSH with different trephine shapes in the mesh (circle versus cross versus slit versus none (Sugarbaker)).
- 7. To estimate the cost effectiveness of commonly used types of mesh (e.g. biologic, synthetic) versus no prophylactic mesh in prevention PSH and improving health related quality of life.

#### 4. Plan of Investigation

#### 4.1 Study schema

#### Figure 1: The study schema for CIPHER (Phase B)

\*The duration of follow-up is for a minimum of 2 and maximum of 4 years

## 4.2 Study design

This is a multi-centre, pragmatic cohort study to follow-up participants from the date of index stoma formation surgery. Follow-up will continue for a minimum of 2 years post-operatively, until closure of the cohort or death.

## 4.3 Setting

We intend to recruit at least 70 NHS acute trusts across the United Kingdom over a period of 12 months.

## 4.4 Study population

The target population is adults (18+ years) undergoing elective or expedited surgery, i.e planned operation, with the intention to form a stoma, irrespective of the primary indication for the planned surgery (e.g. colorectal cancer, inflammatory bowel disease).

## 4.4.1 Inclusion criteria

A participant may take part in the study if **ALL** of the following apply:

- 1. Aged 18 years or over
- 2. Able to give written informed consent
- 3. Undergoing elective or expedited surgery (NCEPOD Classification) to create a stoma; either an ileostomy or colostomy

## 4.4.2 Exclusion criteria

A participant may not enter the study if **ANY** of the following apply:

- 1. Lacking the capacity to consent
- 2. Having urgent or immediate surgery (NCEPOD Classification)
- 3. Previous abdominal wall stoma
- 4. Life expectancy <12 months from the index procedure
- 5. Having surgery with intention of forming a double-barrelled stoma
- 6. Having surgery with intention of forming a urostomy

## 4.5 Interventions and other predictors of outcome to be studied

Phase A of the CIPHER study (REC reference: 16/EM/0155) has defined the key surgical steps of interest. These are:

- 1. Method of forming the stoma trephine;
- 2. Whether, and how, mesh is used to reinforce the stoma trephine;
- 3. Use of the stoma as a specimen extraction site;
- 4. Closure of other wounds formed during the procedure;
- 5. Spouting the stoma lumen.

Details of specific data items are shown in

## Table 1.

## Table 1:Key surgical steps of interest

1. Trephine Formation
Subcutaneous tissue excised
Relationship of the muscle layer incision to the rectus abdominis
Anterior sheath: was a laparoscopic trocar used to puncture the anterior sheath
Size of incision [widest diameter in mm]
Shape of incision
Was any of the anterior sheath removed
Adjustments made to the size of the incision
Sutures used to buttress end of incision
Posterior sheath: was a laparoscopic trocar used to puncture the anterior sheath
Size of incision [widest diameter in mm]
Shape of incision
Was any of the posterior sheath removed
Adjustments made to the size of the incision
Sutures used to buttress end of incision
Muscle fibres separated with blunt dissection
Intra-operative vessel damage - epigastric vessel
Location of trephine in relation to port site (Laparoscopic procedures only)
Reinforcing the Stoma Trephine with Mesh
2. Reinforcing the Stoma Trephine with Mesh
Was mesh used to reinforce stoma trephine
Mesh product code
Mesh cut or adjusted
Diameter of mesh inserted if changed from original [in mm]
Shape of mesh inserted if changed from original
Location of mesh placement
Route used to position mesh
What shape was the keyhole
What size was the keyhole [in mm]
Mesh secured to abdominal wall (including sheath, muscle, peritoneum)
Mesh secured to stoma serosa
3. Use of the Stoma as a Specimen Extraction Site
Stoma trephine used as an extraction site
4. Closure of other Wounds Formed during the Procedure
Main abdominal incision
Biggost post site [in mm]

Closure of deep layer

5. Spouting the Stoma Lumen

Has the stoma been spouted

Participants' characteristics at baseline will be documented, consistent with the variables agreed as potentially prognostic for PSH in the Phase A consensus process when identifying important surgical variations.

SCNs will also document common complications that arise in hospital before discharge (**Table 2**). Complications can be both prognostic for PSH and a secondary outcome (see 4.6.2) reflecting short-term risks.

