## Table 2: Complications

Complication	Mild	Moderate	Severe
Bleeding:	Transfuse	Embolisation (IR)	Return to theatre
Infection - chest:	Antibiotic	Oxygen support	Ventilation / intensive
			care
Infection - urine:	First line antibiotic	Second line antibiotic	Pyelonephritis
Infection - Intra-	Antibiotic	Interventional radiology	Laparotomy
abdominal:			
Wound - infection at	Antibiotic	Interventional radiology	Laparotomy
stoma site:			
Wound - infection at	Antibiotic	Interventional radiology	Laparotomy
	Superficial (skin)	Doop (fascia)	Poturn to theatro
Would coroma:	Drain on ward (achirata)	Interventional radiology	Return to theatre
would - seroma.	Drain on ward (aspirate)	drain	Return to theatre
Wound - haematoma:	Drain on ward (remove wound clips)	Requires antibiotics	Return to theatre
Incisional hernia:	<4cm in size	≥4 and <10cm in size	≥10cm in size
lleus:	<5 days	≥5 days, no IV feeding	IV feeding
Deep vein thrombosis:	Below the knee	Above the knee	Above the knee and extends into the vena cava
Pulmonary embolism:	Diagnosed radiologically, no effect on patient (except anticoagulant)	Endovascular intervention	Formal respiratory support / high care setting
Myocardial infarction:	Pharmacological treatment	Cath lab intervention (PCI)	ICU management
Delirium:	Occurs at night time only	Occurs at all hours	Psychiatric input required
Kidney failure:	IV fluid	Dialysis outside ICU	Dialysis in ICU
Pressure sore:	Grade 1 & 2	Grade 3/4	Surgical intervention
Permanent stroke:			Always severe
Return to theatre:			Always severe
Death:			Always severe
Anastomotic leak:	Antibiotics	Radiology intervention	Return to theatre
Anal/rectal stump	Antibiotics	Radiology intervention	Return to theatre
dehiscence:			
Mucotaneous	Superficial separation at	Involvement of dermis	Full MCJ separation
dehiscence:	the mucotaneous junction	layer leading to increase in	involving fat layer,
	(MCJ), either partial or	width or depth of	requiring primary wound
	circumferential	separation, partial or	dressing (stoma in
Channeller	Tichtening/neuroning.f		cavity/moat)
Stenosis:	the stome orifice no	functioning ribbon like	to dilate
	dilation required	stool	
Prolanse:	Variation in night and day	Persistent increase in	Persistent increase in
	length	length, functioning	length, non-functioning
Retraction:	Stoma partially retracted	Stoma mucosa below skin	Stoma below skin level
	below skin level but	level, managed with stoma	unable to manage with
	manageable with stoma	appliance/accessory	ostomy products

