#### 4.6.2 Secondary outcome measures

Secondary outcomes include:

- 1. Intensive care unit (ICU) stay (days) during admission for index surgery
- 2. Hospital stay (days) during admission for index surgery and associated costs
- 3. Surgical site infection during admission for index surgery and 30 days afterwards
- 4. Other complications, documented using the Clavien Dindo classification [35] and the Comprehensive Complication Index [36, 37]
- 5. Questionnaire to assess symptoms of PSH (developed in Phase A; REC 16/EM/0155)
- 6. Generic health status (EQ-5D-5L, SF12 [38, 39]), which will be combined with survival to estimate QALYs
- 7. Appointments with SCNs, stoma care products used and associated costs
- 8. PSH repair (procedure codes for stoma formation in HES, information from SCNs) and associated hospital costs
- 9. Estimated cost of hospital care during follow up and primary care, social care and societal costs associated with stoma.

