#### Figure 2: Data Collection Diagram

#### Footnotes:

- 1. SCNs will record the number of visits at 6 weeks, 6 months and 6 monthly thereafter; we also intend to obtain these data from the database used locally.
- 2. We intend to obtain data for all visits from the database used locally.
- 3. HES and ONS data should record all hospital activity but will only be extracted periodically.

	Time / frequency of data collection with respect to date of index surgery						
	Before	During	Up to discharge	6-weeks after	6-month after	12-month after	6-monthly to study end
Screening log	~						
Consent form	~						
Participant baseline details	~						
Surgical details		~					
Complications			~				
Index hospitalisation resource use		~	~				
SCN contacts with participants and hospital admissions				~	~	~	~
Exercise, support garment data				~	~	~	
EQ-5D-5L; SF-12	~			~	~	~	~
Wound questionnaire			~	~			
Community-based health care					~	~	~
Stoma questionnaire					~	~	~
Questionnaire about living with a stoma						~	
Request CT scans, taken as part of patient's usual care				~	~	~	~
Stoma care products issued				~	~	~	~
In-patient hospital episodes *					~	~	~
Out-patient hospital episodes *					~	~	~

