## Table 4:Timing and frequency of collection of data items

Footnotes:

\*In-patient and out-patient hospital episodes will be extracted from HES data, which will be requested periodically throughout the study.

Data collection will include the following elements:

- (a) A screening log of patients undergoing elective surgery to form a stoma. This log will be maintained by centres but data from the log will only be entered for eligible patients who consent to take part in the study (i.e. participants).
- (b) Confirmation of patient's eligibility against all eligibility criteria, written informed consent and patient's contact preferences (see below).
- (c) Baseline data characterising participants before surgery will be collected by the SCNs and obtained retrospectively from a HES data extract. Data from these sources will include any relevant diseases and comorbidities the participant may have and their current health status.
- (d) Surgery details will be collected by the surgical team in theatre and entered into an online database. These details will describe how the stoma is formed.
- (e) Details of a participant's recovery after surgery will be collected at discharge by the SCNs and obtained retrospectively from a HES data extract. These details will describe the patients post-operative stay including surgical or medical complications.
- (f) All follow up contacts between a participant and a SCN will be recorded by the SCNs; we also intend to obtain these details from local NHS stoma care databases used by hospitals when available.
- (g) Participants will be asked to complete health questionnaires, i.e. the EQ-5D-5L and SF-12, a purpose-designed questionnaire about stoma symptoms developed in Phase A [34], a questionnaire about how the participant is adapting to living with a stoma [43] and brief questions about primary care, social care and other resource use related to the stoma. Participants will be able to choose to receive the questionnaires by post or to complete them via an online secure website. Subject to their consent, we may also issue reminders to participants about completing questionnaires by text messaging.

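### Graded complications are collected only up to discharge, so the window for secondary outcome 4 varies with each participant's length of stay; give it one fixed period from surgery

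*Protocol*

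**What the plan says.** All references are to the Phase B protocol.

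- **Section 4.5, text after Table 1.** Stoma care nurses complete the graded list in Table 2 for the index stay: "SCNs will also document common complications that arise in hospital before discharge". The next sentence gives the data two roles: "Complications can be both prognostic for PSH and a secondary outcome (see 4.6.2) reflecting short-term risks".
- **Section 4.6.2.** Outcome 4 is "Other complications, documented using the Clavien Dindo classification", together with the Comprehensive Complication Index. It has no time window. Outcome 3 has one: "Surgical site infection during admission for index surgery and 30 days afterwards". Outcome 2 is "Hospital stay (days) during admission for index surgery and associated costs".
- **Table 4.** The complications row has a single tick, in the column that ends at discharge.
- **Section 5.4(e).** Recovery details come from the nurses at discharge and from a retrospective HES extract. Their scope is the index stay: "These details will describe the patients post-operative stay including surgical or medical complications".
- **Figure 2 footnotes.** Nurse data collection continues after discharge: "SCNs will record the number of visits at 6 weeks, 6 months and 6 monthly thereafter". Table 4 adds hospital admissions on the same schedule.
- **Section 8.1.** Complications are a binary outcome analysed by logistic regression. Time at risk is not mentioned.

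**The concern.** A binary outcome compared between groups needs the same opportunity for the event in everyone. Here that opportunity ends on a day that follows surgery, can differ from one participant to the next, and may depend on how the operation went. Two participants with the same course, one discharged before a stoma problem appears and one after, are recorded differently.

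The content of Table 2 adds to this. Several entries can plausibly arise or worsen once the patient is home: stenosis, prolapse, retraction, peristomal skin problems, and "Incisional hernia" graded by size. Their milder grades need not cause an admission, so hospital records would not reliably pick them up.

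At stake is the protocol's graded measure of short-term risk, which a reader will set beside any difference in parastomal hernia between surgical methods. The same data are named as possible predictors of hernia. The primary outcome definition is not affected.

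**Working it through.** The protocol states no figure on this point, so there is nothing to reproduce. The check sets the passages side by side and then asks whether a size can be derived.

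**Step 1: where recording stops.** Section 4.5, Table 4 and section 5.4(e) agree on discharge. The HES component of 5.4(e) covers the same stay, so it does not lengthen the window. The window for participant *i* is therefore the length of stay *d(i)*, which is outcome 2.

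**Step 2: what is recorded after discharge.**

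| Event after discharge | Later route in the protocol | Graded for outcome 4? |
|---|---|---|
| Surgical site infection | Outcome 3; wound questionnaire at 6 weeks (Table 4) | Has its own outcome and window |
| Incisional hernia | Present or absent on usual-care CT (section 5.5) | Not by Table 2 size grade, and only in those scanned |
| Event leading to admission | Nurse reports (Table 4), linked HES (section 5.4(i)) | Not stated |
| Parastomal hernia repair | Outcome 8 | Separate outcome |
| Stenosis, prolapse, retraction or skin problem without admission | Nurse visits, stoma products and the stoma questionnaire from 6 months (Table 4) | No graded record |

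The gap is the last row, plus the unstated status of later admissions.

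**Step 3: direction.** Let *F(t)* be the true cumulative risk by day *t*, the same in two groups. If the groups leave hospital on days *d1* < *d2*, the observed risk ratio is *F(d1)/F(d2)*, which is below 1 whenever events occur between *d1* and *d2*. With one common window *T* it is *F(T)/F(T)* = 1. This requires stay to differ between groups for reasons other than complications.

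**Step 4: can a size be given?** It would need *F*, *d1* and *d2*, and the protocol gives none of them. To show how far the answer depends on assumptions, take discharge on day 5 versus day 10 and equal true 30-day risk of 30%, with *F(t)* = 1 − exp(−*H*(*t*/30)^*k*) and *H* = −ln(0.70) = 0.357. All of these inputs are assumed.

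- Constant hazard, *k* = 1: *F(5)* = 0.058, *F(10)* = 0.112, ratio 0.51. For 30-day risks of 20% to 40% the ratio is 0.51 to 0.52, and 18–20% of 30-day events are captured by day 5 and 36–39% by day 10.
- Front-loaded hazard, *k* = 0.5: *F(5)* = 0.136, *F(10)* = 0.186, ratio 0.73. For 20% to 40% the ratio is 0.72 to 0.74, and 44–47% are captured by day 5 and 60–64% by day 10.
- Day 5 versus day 7: 0.72 to 0.73 with constant hazard, 0.85 to 0.86 front-loaded.
- Equal stays: ratio 1, although later events are still unrecorded in both groups.

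The direction is stable under the Step 3 condition. The size depends wholly on the assumed hazard shape and stays. The model also treats stay as independent of complications, which is unlikely, since a complication can lengthen the stay. None of these ratios is an estimate for this study.

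**The case against.** The strongest reply has four parts.

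1. **The scope is a declared choice.** Complications are described as short-term, and most of Table 2 is early in-hospital morbidity such as bleeding, ileus, delirium, chest infection and anastomotic leak. Retraction or skin problems can also arise before discharge, so listing them does not contradict the window. This stands for what is on the list. It does not justify an end point that differs between participants: a short-term outcome still needs a common end.

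2. **Later data exist.** A reader might infer that late complications go unseen. The table above shows that the documents do not support that: surgical site infection, admissions, hernia repair and incisional hernia on CT all have a later route. What remains is narrower, namely no graded record of non-admitted stoma problems and no statement that later admissions count. Section 13.2.3 ties NHS Digital data to the cost analysis, but sections 4.6.2 and 5.4(e) use HES for other purposes too, so that sentence does not exclude them.

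3. **Bias is not shown.** A reader might infer that a technique followed by earlier discharge will look safer. That needs stay to differ between the compared variants. The documents give no evidence of it, and section 8.4 puts mesh insertion at 5–10 minutes of the procedure. This objection stands in full as regards size and net direction.

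4. **The statistical analysis plan may define the window.** It can define the outcome and allocate data sources. It cannot recover graded post-discharge events that no form collected.

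It is also tempting to say that mesh harms in particular are lost at discharge. Table 2 has no mesh-specific item at any time point, so the window is not the reason, and repeating the list would not supply one.

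**Conclusion.** The point holds in a limited form. Graded complications stop at discharge in three concordant places, so the observation window equals length of stay, while the neighbouring infection outcome is followed beyond the admission. Post-discharge stenosis, prolapse, retraction and peristomal skin problems without admission have no graded record, and the role of later admissions in outcome 4 is not stated.

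Incomplete recording after discharge follows from the text alone. Distortion of a comparison is conditional on stay differing between surgical variants, which is not shown. Its size cannot be computed from the protocol, and its net direction is uncertain because complications can prolong stay. This is a worthwhile, inexpensive correction to a secondary outcome, not a threat to the primary result.

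**What to change.** - In section 4.6.2, define outcome 4 over one fixed period counted from index surgery for every participant, for example 30 days or to the 6-week contact. Counting from surgery avoids any dependence on the discharge date.
- Repeat the stoma and wound items of Table 2 at the 6-week stoma care nurse contact, and add the matching tick in Table 4.
- State that readmissions and returns to theatre within the window count, using the planned HES extracts and the nurses' admission reports.
- Keep pre-discharge complications as a descriptive subset.

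The cost is about one extra form page at a contact that already takes place, a little nurse time, and some missing data for participants not seen at 6 weeks. No care is changed. For participants already past that contact, only the record-based part can be applied, and the report should say so.
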